8.3.3 Validity and Reliability

The process for collection of samples for qPCR testing of talimogene laherparepvec DNA among patients, close contacts, and HCPs will follow the Prescribing Information approved by the local health authorities. Further details are available in the Post-Marketing Instruction Manual for IMLYGIC Surveillance Program.

Page 24 of 62

Protocol Number: 20130193
Date: 12 October 2022
Page 25 of 62

8.4 Data Sources

Screening, baseline, and follow-up patient data will be transcribed into the eCRF whenever possible.

8.5 Study Size

The total number of patients who will participate in this study will be determined by the number of patients with post-market use of IMLYGIC who consent to and are deemed eligible to participate in this study. For a sample size to provide an 80% probability of detecting a true event rate of 3 herpetic infections with detection of talimogene laherparepvec DNA per 1000 patients-years, 535 patient-years of follow-up are needed (Table 2). To observe 535 patient-years, accounting for a 5-year study and length of follow-up based on historical mortality data (~2 years mean duration of survival), and because patients may withdraw consent, the projected total number of patients needed to enroll is estimated to be approximately 300. Based upon observed loss to follow-up of the first 82 patients enrolled (6%), the projected enrollment number is adjusted to complete study with 535 patient-years. If no events of herpetic infection with detection of talimogene laherparepvec DNA occur, the precision at the upper 95% confidence level for the true incidence rate is 6.9 events per 1000 patient-years.

Table 2. Statistical Power Provided by Enrollment Target Scenarios

Patient-years	If true event rate is 1 per 1000 patient-years, Upper confidenteriors probability that at least bound of events		Projected number enroll to obtain p	atient-years of
of follow-up in 5-year study	one event will be observed ^a	1000 patient-years if 0 events observed ^b	2-year patient survival ^c	3-year patient survival ^d
275	56%	13.4	154	108
350	65%	10.5	196	138
475	76%	7.8	266	187
535	80%	6.9	300	210
650	86%	5.7	364	256

^a Model of rare events for Poisson distribution with parameter = > 0, if for k = 0, 1, 2,... the probability to observe k events is given by:

$$Pr(X = k) = \frac{(\lambda m)^k e^{-(\lambda m)}}{k!}$$

Where λ is the event rate, m is the number of patient-years, the chance of observing k or more events is: $1 - \Pr(X \le k - 1)$

^b Standard one-tailed 97.5% confidence interval from the Poisson distribution, available at: handbook.cochrane.org/chapter_16/16_9_4_confidence_intervals_when_no_events_are_observed.htm

Amgen Proprietary - Confidential

Product: IMLYGIC®

Protocol Number: 20130193 Date: 12 October 2022

^c Assumes patient survival of 2 years, plus 15% more patients for additional loss to follow-up.

8.6 Data Management

8.6.1 Obtaining Data Files

Data capture is planned to be electronic:

Patients

- Each patient will be assigned a unique identification number at enrollment.
- Data from patients will be entered by site staff into an electronic database provided by the sponsor.

Close contacts and HCPs

• Data will be acquired from the Postmarketing IMLYGIC Surveillance Program.

Amgen representative(s) are responsible for contacting and visiting the Investigator for the purpose of inspecting various records of the study (eg, eCRFs and other pertinent data), provided that patient confidentiality is respected.

The Clinical Monitor or designee is responsible for checking entries in the eCRFs at regular intervals throughout the study to verify adherence to the protocol as well as the completeness, accuracy, and consistency of the data. In accordance with local laws and regulations, the Clinical Monitor or designee is to have access to patient medical records and other study-related records that are needed to verify entries on the eCRFs.

The Investigator agrees to cooperate with the Clinical Monitor or designee to ensure that any problems detected in the course of these monitoring visits, including delays in completing eCRFs, are resolved.

8.6.2 Review and Verification of Data Quality

Upon receipt of data from study sites, Amgen will check the data for potential errors and inconsistencies. The data will be evaluated for potential outliers, missing information, and logical consistency with the study variables. Sites will be queried for clarification if unlikely values, potential errors, or inconsistencies are identified.

8.7 Data Analysis

8.7.1 Planned Analyses

8.7.1.1 Interim Analyses

During data collection, annual study progress reports will be completed for inclusion in Periodic Safety Update Reports. These interim analyses will report on study recruitment (eg, number of patients enrolled), study conduct (eg, patient-years of observation), and

Page 26 of 62

^d Assumes patient survival of 3 years, plus 15% more patients for additional loss to follow-up.

the primary and secondary endpoints assessed at that point in time. Additional ad hoc analysis may be conducted if required for submission to regulatory authorities.

8.7.1.2 Final Analysis

The final analysis will be completed once all enrolled patients have had the opportunity to contribute 5 years of observation.

8.7.2 Planned Method of Analysis

8.7.2.1 General Considerations

This study is descriptive in nature and no formal hypothesis will be tested. Select summaries will also be presented **by** region.

This study will estimate incidence rate of herpetic infection. The incidence rate will be calculated as the number of events divided by sum of follow-up time in patient-years.

8.7.2.2 Missing or Incomplete Data and Lost to Follow-up

Missing data will not be imputed.

Lost to follow-up will be characterized by median duration of observation for study population and reasons for loss to follow-up will be tabulated (mortality, no response from patient, withdraw of consent, or other).

8.7.2.3 Descriptive Analysis

8.7.2.3.1 Description of Study Enrollment

Based on the numeric tally of patients in screening log, the proportion of patients enrolling in the study will be summarized.

To describe if study patients are representative of the broader population of IMLYGIC patients, all patients in the screening log and the study patients will be reported by proportion for these variables: sex, age, **race**, **ethnicity**, and disease stage.

8.7.2.3.2 Description of Patient Characteristics

The study population will be characterized by sex, age, **race**, **ethnicity**, ECOG performance status, disease stage, history of herpetic infections, and previous melanoma therapy.

8.7.2.4 Analysis of the Primary and Secondary Endpoints

8.7.2.4.1 Analysis of the Primary Endpoint

Incidence of herpetic infection with detection of talimogene laherparepvec DNA
among patients. Herpetic infection includes oral herpes, genital herpes, herpetic
whitlow or herpetic gladiatorum of the skin, ocular herpes, herpetic encephalitis, and
disseminated herpetic infection.

The incidence rate will be calculated as the number of suspected herpetic infections that are detectable for talimogene laherparepvec DNA divided by sum of follow-up time (last date of follow-up minus the date of first IMLYGIC dose) in patient-years. As a measure of precision, a 95% confidence interval will be calculated around the incidence rate.

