An important and logical consideration in the use of IMLYGIC is the potential risk of primary infection and reactivation of the virus in patients, as well as the risk of viral transmission from patients to close contacts (close contacts include household members, caregivers, sex partners, and persons sharing the same bed) and HCPs. To assess this risk, preclinical and clinical studies have assessed the biodistribution and shedding, as well as potential for transmission of IMLYGIC. In preclinical models, the biodistribution of IMLYGIC appears to be predominantly restricted to tumor, blood, and tissues that may be associated with immune-mediated viral clearance (spleen, lymph node, liver). In the clinical setting, biodistribution and shedding were initially studied in the first-in-human study (Hu et al, 2006); in this study viral DNA was never detected outside of the occlusive dressing. No viral DNA was detectable in either blood or urine past 1 week after each dose.

Furthermore, biodistribution and shedding of IMLYGIC in IIIB and IVM1c melanoma patients was investigated in a phase 2, single-arm study. The final analysis showed that consistent with the method of administration, talimogene laherparepvec DNA was detected with greatest frequency in swabs of injected lesions (49% of samples in 100% of subjects) and blood (35% of samples in 98% of subjects). Live virus was not detected among 1085 swabs of the exterior of occlusive dressings. Thirty-seven swabs of lesions suspected herpetic origin were taken from 19 subjects, 4 swabs from 3 subjects had

Page 18 of 62

Amgen Proprietary - Confidential

Product: IMLYGIC®

Protocol Number: 20130193 Date: 12 October 2022

detectable talimogene laherparepvec DNA, but all were negative for viral infectivity by TCID50 assay (www.clinicaltrials.gov, NCT02014441).

Consistent with the above findings, among study subjects in the clinical trials to date, no cases of confirmed symptomatic herpetic infection or cases of secondary transmission from IMLYGIC have been reported. During the phase 3 registrational study, 16 herpetic events were reported among subjects who received IMLYGIC; 14 events were reported as cold sores, one as HSV-1 infection, and one as herpetic keratitis. However, none of these lesions were tested for IMLYGIC, and there was no pathologic confirmation of a herpetic infection. For additional information, please refer to the IMLYGIC Investigator's Brochure.

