8.9 Limitations of the Research Methods

8.9.1 Internal Validity of Study Design

Identification of the primary endpoint, incidence rate of herpetic infection with detection of talimogene laherparepvec DNA among patients enrolled in Study 20130193 may be susceptible to measurement error because suspected cases of herpetic infection in the real world may be infrequently brought to medical attention. Herpetic infection data retrieved from the study will be collected in a rigorous manner, and the patients themselves will be an important source of information. Targeted education and training linked to the Prescribing Information will ensure that patients and Investigators are aware of the signs and symptoms that may indicate herpetic infection and of the need for timely reporting for sample collection. These study procedures for identifying herpetic infection are built upon approaches for data collection within clinical studies of herpes simplex vaccine (Belshe et al, 2012), natural history studies of HSV (Mark et al, 2008; van Velzen et al, 2013), and the pharmacovigilance program for varicella vaccine in Europe and United States (Galea et al, 2008; Goulleret et al, 2010). However, unlike the study population with a grievous illness, these prior approaches were conducted in generally healthy populations. As an indicator of how well patients are reporting suspected herpetic infection, it is anticipated that study patients should report infection within the range of occurrence for the general population (ie, frequent recurrences of

Protocol Number: 20130193

Date: 12 October 2022 Page 32 of 62

oro-labial lesions are reported by 3% to 5% of the general population (Rooney et al, 1993).

8.9.2 **External Validity of Study Design**

Generalizability of study results may be limited by use of a study population based on a convenience (ie, not random) sample of study sites participating in the Postmarketing IMLYGIC Surveillance Program. Study sites that are selected will be among those with the earliest adoption of IMLYGIC. While the study patients will be recruited from these study sites, the patient inclusion and exclusion criteria are limited to best reflect any use of IMLYGIC in real-world, clinical practice. To describe if the Study 20130193 patients are representative of broader population of IMLYGIC patients, all patients in the screening log and the study patients will be reported by proportion for sex, age, and disease stage.

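### Reported suspected infections that are never tested by qPCR enter the primary rate as negatives, so the 80% and the 6.9 per 1000 bound describe reported and tested infections, not the true rate

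*Protocol*

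**What the plan says.** **Estimator.** Protocol 8.7.2.4.1 defines the primary rate as the count of suspected infections that are "detectable for talimogene laherparepvec DNA divided by sum of follow-up time", with follow-up for each patient equal to "last date of follow-up minus the date of first IMLYGIC dose". Section 8.7.2.2 adds: "Missing data will not be imputed".

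**How a test comes about.** Under 8.2.5, a patient with a suspected lesion should seek care and have it swabbed, either for product DNA through the surveillance programme or for wild-type HSV-1 by local practice. No sampling is scheduled. After treatment ends, contact is every 3 months, by phone or at a routine visit. Table 1 footnote h collects, for each reported episode, whether and how it was tested.

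**Precision.** Section 8.5 gives an 80% probability of detecting a true rate of 3 per 1000 with 535 patient-years. If no events occur, it says "the precision at the upper 95% confidence level for the true incidence rate is 6.9 events per 1000 patient-years". The footnotes to Table 2 allow 15% extra patients for loss to follow-up and nothing for incomplete testing.

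**Acknowledged weakness and its check.** Section 8.9.1 concedes that "suspected cases of herpetic infection in the real world may be infrequently brought to medical attention". As an indicator of reporting it expects that "study patients should report infection within the range of occurrence for the general population", and it takes that range from the 3% to 5% of people with frequent oro-labial recurrences.

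**The concern.** The numerator needs a positive product-DNA result, but the denominator is all follow-up whether or not suspected episodes were tested. With no imputation, an untested episode is in effect imputed as no event. Untested episodes are foreseeable: testing depends on the patient seeking care in time, and an episode may have only a local wild-type test. In the phase 3 study described in 6.2, 16 herpetic events were reported and "none of these lesions were tested for IMLYGIC, and there was no pathologic confirmation of a herpetic infection".

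The study is a regulatory safety requirement, and zero events is a plausible headline result. Zero events with every suspected lesion tested would be reassuring. Zero events with few lesions tested would say little. Under the stated analysis both would be reported as 0 events with an upper limit of 6.9 per 1000 at the planned follow-up.

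**Working it through.** **1. Treatment of an untested episode.** A reported episode with no qPCR result contributes 0 to the numerator, and its person-time stays in the denominator. This is the same contribution as a tested negative.

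**2. Reproducing 8.5.** Inputs from 8.5 and Table 2: rate 3 per 1000, 535 patient-years, one-sided 97.5% Poisson limit.
- Expected events: 0.003 × 535 = 1.605.
- P(at least one event) = 1 − exp(−1.605) = 79.9% (stated 80%).
- Zero-event bound: −ln(0.025) / 535 = 3.689 / 535 = 6.90 per 1000 (stated 6.9).

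Both figures are right as calculations.

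**3. Incomplete ascertainment.** Let p be the fraction of true product-DNA infections that are both reported and tested. Ascertained events have mean 1.605p, so P(at least one) = 1 − exp(−1.605p), and the zero-event bound on the true rate is 6.90/p. The protocol gives no value for p; the values below are assumptions.

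| p (assumed) | P(at least one event) at 3 per 1000 | Zero-event bound per 1000 |
|---|---|---|
| 100% | 79.9% | 6.9 |
| 75% | 70.0% | 9.2 |
| 50% | 55.2% | 13.8 |
| 25% | 33.1% | 27.6 |

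**4. Untested is not the same as negative.** In the phase 2 study in 6.2, 4 of 37 swabs of suspected lesions (3 of 19 subjects) had detectable product DNA. If 15 episodes went untested and that positivity applied, the events missed would be 15 × 4/37 = 1.6 or 15 × 3/19 = 2.4. With 2 events the exact upper limit is 7.225 / 535 = 13.5 per 1000. This is an illustration, not a forecast.

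**5. The check in 8.9.1.** With about 300 patients, 3% to 5% is 9 to 15 patients. All of them could report an episode and none be swabbed, and the check would still be met. It also sets any reported infection against the share of people with frequent recurrences, a subset of those with infections. Section 6.2 gives HSV-1 seroprevalence of 54% at ages 14 to 49. Considerable under-reporting could therefore fall inside the range.

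**The case against.** **The figures match the stated endpoint.** The objective, the endpoint and the sizing all refer to infection with product DNA detected, and for infections that are reported and tested 80% and 6.9 are correct. This stands. A reader might infer that 8.5 is miscalculated; it is not. What fails is calling the bound a limit on the true incidence rate without a condition.

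**The size is unknown.** No document gives a tested fraction. The untested phase 3 events are a precedent, not a prediction, and the phase 2 study did swab suspected lesions. The present study has a dedicated qPCR route that also accepts suitable office swabs, asks about symptoms at every assessment, and trains patients and investigators. This stands, and it is why the values of p are illustration only.

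**DNA detection may overcount.** The four positive phase 2 swabs were all negative for infectivity, and such results would count as events here. That matters for interpreting the endpoint clinically, but it does not offset missed DNA-positive episodes when the endpoint is DNA detection.

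**Other outputs give indirect signals.** Adverse events, antiherpetic use and wild-type HSV-1 rates are planned, so an absence of testing would not be wholly invisible. None of them gives the number of suspected episodes left untested.

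**This may belong in the SAP.** Tabulations and sensitivity analyses often do, and the SAP is not shown. But the estimator, the no-imputation rule and the unconditional wording of 8.5 are all fixed in the protocol.

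**The 3% to 5% figure was offered only as a check on reporting.** That is fair. Even for reporting, however, it is a weak standard, and no stated check covers testing.

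**Conclusion.** The point holds in a limited form. For reported episodes, the protocol's estimator treats untested as negative, so the rate and its upper limit are too low to the extent that those episodes carried product DNA. The direction follows from the definition; the size cannot be determined from the protocol. The 80% and 6.9 per 1000 are best-case values that need complete reporting and testing. Under assumed ascertainment of 75% to 25%, they become 70% to 33% and 9.2 to 27.6 per 1000.

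Two stronger readings should be resisted. A reader might infer that the study will observe p, so that 6.9 can be replaced by 6.9/p. It will observe only the tested share of reported episodes; unreported infections, and the DNA status of untested lesions, stay unseen. A reader might also infer that a better reporting benchmark would expose non-testing. No reporting benchmark can; only the tested fraction does.

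**What to change.** 1. **8.7.2.4.1:** from the Table 1 footnote h data, report the numbers of suspected, swabbed and qPCR-resulted episodes, during and after treatment.
2. **8.7.2.4.1:** give the primary rate with its 95% CI in three versions: untested reported episodes counted as negative (the primary analysis, unchanged); at the positivity seen in tested episodes, stating the assumption that testing is unrelated to DNA status; and all positive. The last is an extreme bound, not an estimate: 15 untested episodes would give 15/535 = 28.0 per 1000 if no tested episode were positive.
3. **8.5:** state that 80% and 6.9 per 1000 assume every product infection is reported and tested. Do not substitute a figure based on an observed tested fraction.
4. **8.9.1:** stop using 3% to 5% as evidence of adequate reporting. Optionally compare observed episodes with those expected from each patient's baseline recurrence frequency (Table 1 footnote g), labelled as a check on reporting only. Use the tested fraction from item 1 as the check on testing.

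The cost is a few extra tables from data already collected, with no new study procedure, and a precision statement that becomes conditional and less favourable.
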